- H4: Those in the self-directed modification group will exhibit smaller average changes in FPA compared to those in the conventional gait modification group. However, those in the self-directed modification group will report lower ratings of difficulty in performing the modification, compared to the specific-target gait modification group.
- H5: Both groups will exhibit improvements in biomechanical (e.g. knee adduction moment) and clinical outcomes (e.g. knee pain, physical function) at follow-up, compared to baseline.
- H6: Biomechanical (e.g. knee adduction moment) and clinical outcome (e.g. knee pain, physical function) change scores from baseline to follow up will not differ between groups.

Participants

Adults with knee OA will be recruited and randomized into two treatment arms. All eligible

participants will: 1) be 50 years of age or greater, 2) exhibit signs of tibiofemoral OA (a score of ≥ 2 on the Kellgren and Lawrence (KL) grading scale [1]) predominantly in the medial compartment, 3) self-reported knee pain $\geq 3 / 10$ on a numerical rating scale of pain (NRS; 0 = “no pain” and 10 = “worst pain imaginable”) during most days of the previous month, 4) are comfortable walking intermittently for 30 minutes, and 5) fit into the available sizes of sensorized shoes (sizes spanning US women’s 5 to men’s 13).

Exclusion criteria include: 1) any knee surgery or intraarticular injections within the past 6 months, 2) a history of joint replacement surgery or high tibial osteotomy, 3) current or recent (within 6 weeks) corticosteroid injections, 4) use of a gait aid, 5) currently on a wait list for joint replacement surgery or high tibial osteotomy, 6) any inflammatory arthritic condition, 7) any other conditions that may affect normal gait or participation in an aerobic exercise program, and 8) cannot attend all required appointments at UBC. Additionally, potential participants will undergo an initial gait screening similar to a recent study [2] (details are outlined below), with the goal of identifying participants who are capable of reducing their KAM magnitude when FPA is modified. This gait screen will examine both natural walking FPA and changes in knee load while walking with increased toe-in and toe-out. Those who do not elicit a reduction in KAM impulse $\geq 5\%$ when FPA is changed by 10° in either direction will be excluded from the study as they would be considered non-responders.

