A total of 36 individuals will be recruited for this study, 18 in each group. Approximately 60% in each group will be female. The primary outcome measure of this study is the change in absolute FPA performance error (the difference between the performed and the targeted FPA), which is indicative of how ‘accurate’ the patient is when performing the modification. This outcome measure is only relevant to the SMOD group, who have a specific target for their modification; therefore, allowing an error value to be calculated. This outcome will be measured during immediate and delayed retention at week one compared to follow-up and will provide evidence of the extent to which motor learning has occurred. Previous FPA performance error during immediate retention testing after a six-week FPA modification resulted in a small effect (Cohens $d = 0.35$) [3]. We are also interested in exploring the clinical and biomechanical differences between the SMOD and AMAC gait modification groups; however, no study has previously compared these methods of gait modification. Therefore, we will be conservative and base our sample size calculation on the between-within interaction effect of a 2×4 (group = 2: SMOD vs AMAC; measure = 4: immediate and delayed retention tests at week 1 and follow up) repeated measures ANOVA with an effect size of $f = 0.175$ ($f = d / 2$). With power = 0.8 and alpha = 0.05, a total sample of 30 is required [4]. With a conservatively estimated attrition of 15%, we will recruit 36 participants total (18 per group).

Procedures

Recruitment and screening

Volunteers will be recruited via print and social media, and via our database of previous participants who have indicated interest in participating in future studies. Interested volunteers will be screened via phone, email, or our lab website by the study coordinator to assess inclusion and exclusion criteria. Those deemed preliminarily eligible will be invited to attend a gait screening appointment. Eligible participants who pass the gait screen will be referred for a radiographic assessment of their knees to confirm the presence of structural signs of knee OA.

Standing, semi-flexed posteroanterior radiographs of both knees will be taken. A trained assessor will grade all radiographs based on the KL criteria. Those passing all screening requirements will be invited to enroll in the study.

Gait screening

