The gait screen will be performed using motion capture to measure self-selected FPA, joint angles, and joint moments during over-ground walking. Fifty-two retroreflective markers will be placed on the skin over boney landmarks and 14-high speed cameras (sample rate = 100 Hz) will track the positions of these markers in three dimensions. Additionally, two floor-mounted force platforms (sample rate = 2000 Hz) will measure ground reaction forces during walking. Natural walking trials across the 10m instrumented walkway will be performed first (one length equals one walking trial), followed by toe-in and toe-out walking. The latter will be guided verbally such that several walking passes are completed at a range of FPA magnitudes (small toe-in/out, medium toe-in/out, and large toe-in/out). The specific amount of change in FPA is not relevant, as long as a range of FPA magnitudes are recorded over the collected walking trials. These data will be used to determine whether the participant is a responder to FPA modification, and which direction (toe-in or toe-out) elicits the greatest response. The threshold of a 5% reduction in the knee adduction moment impulse (area under the knee adduction moment – time curve) with a 10° change in FPA will be used to determine response. For recruitment purposes, those who respond to either toe-in or toe-out ($\geq 5\%$ reduction with a 10° change in FPA) will be provided this FPA modification. For those who elicit response to both, the modification (toe-in or toe-out) with the greatest reduction per 10° of change in FPA will be used in the intervention. This cutoff value is conservative, allowing for some regression in response while still maintaining overall reduced KAM impulse. A 5% threshold was chosen as the average reduction in KAM impulse after a 16 week toe-out modification program was 4.7% [5]. These methods of screening for response to FPA change and personalizing the direction of FPA change were shown to improve biomechanical outcomes relative to a non-personalized approach [6, 7].

Baseline and follow-up data collection

An identical baseline and follow-up gait assessment, separated by seven weeks, will be conducted in the laboratory, and using both optical-motion capture and the sensorized shoe system. These assessments will include questionnaires, a timed stair climb, and gait analysis.

A) Patient reported outcomes and physical function

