Official Title: Foot progression angle modification: an exploratory six-week intervention in people with knee osteoarthritis.

NCT Number: TBD

Document Date: Mar 24th, 2020

Statistical Analysis Plan

Statistical analyses will be performed by an independent statistician. Means and standard deviations will be calculated for each outcome measure and baseline demographic characteristic. Baseline demographic data (e.g. age, body mass index, disease severity) will be examined for between-group differences using unpaired two-tailed t-tests. For all statistical analyses, alpha will be set to 0.05. Any multiple pairwise comparisons will be adjusted using the Bonferroni correction method.

Data will be assessed for sphericity, homoscedasticity, and normality using Mauchley's test, residual versus predicted plots, and quantile-quantile plots. Homoscedasticity and normality assumptions will be confirmed using Levene's test and Shapiro-Wilk's test, respectively. Sphericity assumption violations will be corrected for using the Greenhouse Geisser approach. Violations of homoscedasticity will be corrected for by bootstrapped model parameters. If normality is not met, a non-parametric test will be used.

Primary Hypotheses:

Repeated measures analyses of variance (ANOVA) will be performed to examine the within-group changes in learning outcomes over the six-week intervention. Between-group differences will be examined using a two-way mixed ANOVA, with the repeated measure being the learning outcome (foot progression angle change from baseline during in-lab and at-home walking) and the between-subject factor being group assignment (SMOD vs AMAC).

Secondary Hypotheses:

Biomechanical (knee joint moments), clinical (NRS knee pain, KOOS pain, symptoms, and physical function scores), and difficulty (difficulty of performing the FPA modification) change scores will be examined using an analysis of covariance (ANCOVA) with significant between-group baseline demographic group differences and baseline outcome values included as covariates.

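### Week-7 NRS and KOOS are scheduled only within the laboratory visit, so anyone who misses that visit drops out of the clinical comparison by default

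*SAP*

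**What the plan says.** H5 predicts improvement in both arms from baseline to follow-up, and H6 predicts that change does not differ between arms (Protocol, Secondary Hypotheses). Both cover biomechanical and clinical outcomes.

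On timing and place, Protocol, Baseline and follow-up data collection, states: "An identical baseline and follow-up gait assessment, separated by seven weeks, will be conducted in the laboratory". Questionnaires, stair climb and gait analysis all belong to that assessment. Subsection A lists the NRS for average pain over the previous week and the KOOS among the questionnaires. No other collection of the week-7 NRS or the KOOS is described.

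On expected loss, Protocol, Participants, states: "With a conservatively estimated attrition of 15%, we will recruit 36 participants total (18 per group").

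On analysis, SAP, Secondary Hypotheses, states that "change scores will be examined using an analysis of covariance (ANCOVA"), adjusted for the baseline value and for baseline demographics that differ significantly between groups. The SAP has rules for violations of sphericity, homoscedasticity and normality. Neither document defines an analysis population, a method for missing outcomes, a sensitivity analysis, or a way to obtain questionnaires from someone who does not come to the follow-up visit.

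**The concern.** A change score needs both values. Without the week-7 value, an ANCOVA of change omits the participant, and nothing in the plan would lead to a different result. The clinical comparison then describes those who attended the visit rather than those randomised.

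This matters if attendance is related to outcome. People for whom the modification was painful or hard may be less likely to return and may also have done worse on pain and function. Leaving them out would flatter each arm's mean change. If the arms lose different numbers, the between-arm comparison is affected too. H4 makes unequal loss conceivable, because it expects that "those in the self-directed modification group will report lower ratings of difficulty in performing the modification" than those given a fixed target.

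The gap is avoidable for these outcomes. NRS and KOOS are self-reported, and participants already record pain scores at home during the intervention (Protocol, Gait modification intervention). A week-7 value that was not requested at the time cannot be recovered later.

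**Working it through.** **Inputs from the documents.** Required total 30; recruited 36, 18 per arm; attrition allowance 15% (Protocol, Participants). One follow-up at seven weeks (Protocol, Baseline and follow-up data collection).

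**Inputs assumed, not in the documents.** Mean change in those lost is g = 1, 2 or 3 NRS points worse than in attenders, and this gap is not explained by baseline. SD of NRS change 2; correlation with baseline 0.5. Illustrative unequal split: 4 of 18 lost in SMOD, 1 of 18 in AMAC.

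**1. The plan's own figure.** 30 / (1 − 0.15) = 35.3, rounded up to 36. This reproduces. Expected loss at that rate is 0.15 × 36 = 5.4 people. Recruiting 36 rather than 30 protects the number analysed. It does not change who is in the analysis.

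**2. Within-arm mean change (H5).** If a fraction p of an arm is lost and those lost improve by g less, the attender mean exceeds the all-randomised mean by p × g. With equal loss, p = 0.15:

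| g | overstatement of improvement |
|---|---|
| 1 | 0.15 |
| 2 | 0.30 |
| 3 | 0.45 |

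With whole people, 3 of 18 per arm, p = 0.167 and the range is 0.17 to 0.50.

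**3. Between-arm difference (H6).** The shift is g × (k_SMOD − k_AMAC) / 18. With equal loss it is zero. With 4 versus 1 it is g × 3/18:

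| g | shift in favour of SMOD |
|---|---|
| 1 | 0.17 |
| 2 | 0.33 |
| 3 | 0.50 |

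**4. Scale.** Residual SD = 2 × √(1 − 0.5²) = 1.73. With about 15.5 attenders per arm, SE = 1.73 × √(2/15.5) = 0.62. The shifts are therefore 0.27, 0.54 and 0.80 SE.

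**5. Direction relative to H6.** Let δ be the true SMOD-minus-AMAC difference in improvement and b the shift. The attenders-only comparison estimates δ + b. If δ = 0 and b = 0.33, it shows a false SMOD advantage of 0.33, which is away from H6. The estimate is closer to zero than the truth only when δ < −b/2, here when SMOD is truly worse by more than 0.17 points.

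**6. Precision.** For an ANCOVA with one covariate, two-sided 5%, the 95% CI half-width is 0.75 residual SD with 15 per arm and 0.68 with 18 per arm. The difference detectable with 80% power goes from 1.06 to 0.96 residual SD. Full questionnaire return would bring a modest gain here as well.

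**The case against.** The strongest reply is that the plan never says it will analyse attenders only. That is correct. Restriction to attenders follows from silence, and the point should be worded as a default.

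A reader might infer several stronger things that the documents do not support:

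- *Stopping the sessions means having no follow-up.* Nothing makes the week-7 assessment conditional on completing the sessions, and nobody is withdrawn for missing them. The problem concerns those who do not attend the visit.
- *The plan forecasts that 15% of questionnaires will be missing.* The 15% is an allowance, described as conservative, added to a sample size built on the retention tests. It is the only loss figure available, but it is not a prediction for NRS or KOOS. The exclusion of people who cannot attend all appointments may keep actual loss lower.
- *The clinical outcomes have no scoring rule.* The NRS is defined with anchors and recall period, and the KOOS is referenced. Only the handling of a missing value is absent.
- *The omission pushes H6 towards its predicted result.* Step 5 shows that this depends on the true difference. H4 concerns difficulty ratings and says nothing about dropout, so unequal loss remains an assumption.

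It is also fair that the SAP's ANCOVA compares groups and that no separate within-group test is given for clinical outcomes. For H5 the overstatement applies to any mean change formed from those with both values. Finally, the trial is exploratory, these hypotheses are secondary, and the primary outcome is untouched. All of that limits the weight of the point. It does not remove it, because the remedy is cheap and acts on data that would otherwise never be collected.

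**Conclusion.** The point holds as a gap in data collection and analysis for the self-reported outcomes of H5/H6. With NRS and KOOS tied to one laboratory visit and no rule for a missing follow-up, non-attenders leave the clinical comparison by default, at the plan's allowance about 5 of 36.

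The size is moderate and conditional. It rests on an assumed deficit of 1 to 3 NRS points in those lost and, for the between-arm shift, on the 4 versus 1 split. Expressing that shift as 0.27 to 0.80 SE further assumes SD 2 and correlation 0.5. If loss is unrelated to outcome there is no bias, and if loss and deficit are equal across arms only the within-arm means are affected.

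The documents do not support a claim that the trial is biased towards finding no difference, or that the SAP prescribes a completers analysis. The change is worth making before follow-up data are collected.

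**What to change.** **Protocol, Baseline and follow-up data collection:** add that every randomised participant, including anyone who stops the sessions or cannot attend the laboratory, is asked for the week-7 NRS and KOOS by phone, mail or online form.

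**SAP, Secondary Hypotheses:** add that clinical outcomes are analysed in the randomised arm using all week-7 values however collected, with the attenders-only ANCOVA as a sensitivity analysis. Report the number without a week-7 value by arm.

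**Values still missing:** any use of the daily or session pain scores to fill a missing NRS should be a sensitivity analysis only. Those items differ from the previous-week average, they may stop when the participant stops, and an imputation model would rest on about 15 people per arm. They offer no direct substitute for KOOS.

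**Laboratory outcomes:** label joint moments and stair-climb time as available for attenders only.

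**Cost:** a short addition to each document and contact with about five people. The downside is that a few NRS and KOOS values come by a different mode from the rest; record the mode so that it can be examined.

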Stair ascent and descent will be performed while wearing the sensorized shoes. This will take place at a building nearby the laboratory (5-minute walk) because of the availability of continuous linear sets of stairs for multiple flights. This allows the use of the sensorized shoe for measuring FPA during stair ascent and descent. These FPA data will be compared with transfer test data (details included below) examined at several points throughout the intervention. These same shoes will be provided to the participant to measure real-world FPA during at-home and community walking.

Sensorized shoes

A custom inertial sensor consisting of a 3-axis accelerometer (signal range: $\pm 4g$), gyroscope ($\pm 500^\circ/s$), and magnetometer ($\pm 1200\mu T$), sampling data at 100 Hz will be embedded in the sole of the shoe. A previously published custom sensor fusion algorithm [13], programmed into a microcontroller, calculates the FPA in real time and stores it on a microSD card for later extraction. The sensorized shoe design and algorithm has been validated during treadmill [14] and over-ground walking [15] with excellent validity and reliability (absolute error = 1.7° and intraclass correlation coefficients > 0.9).

Randomization

Once deemed eligible and baseline data collection is complete, each participant will be randomized to either the SMOD or AMAC group. Randomization will be performed using an *a priori* block-stratified approach based on sex and KL grade. A predetermined randomization matrix will be computed [16] by a team member not involved in testing or the intervention. Group allocations will be stored in opaque envelopes, which will be opened in a sequential manner after baseline testing and before the first practice session. The group allocation will be communicated to the study trainer via email.

Gait modification intervention

Both groups will attend six practice sessions conducted weekly, which will last approximately 1 hour each. Walking practice will be conducted on a treadmill with a full-length mirror placed

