During each practice session, participants will be asked to rate their knee pain at the beginning, middle, and end of the session using an 11-point numerical rating scale (0 = “no pain” and 10 = “worst pain imaginable”). At the end of the sessions, they will be asked to rate the difficulty in achieving their FPA modification during that practice period using an 11-point numerical rating scale (0 = “not difficult” and 10 = “most difficult/unable to perform”).

An instructional booklet will be provided which outlines details of how to care for and use the sensorized shoes while at home and in the community. Participants will track daily walking volume, walking times on each day, daily knee pain using an NRS (e.g. overall pain, pain during walking), non-walking exercise activities, and any adverse events related to their knees or walking. Additionally, an 11-point numerical rating scale will be used to report weekly confidence in how accurately the FPA modification was performed (0 = “no confidence at all/unable to perform” and 10 = “completely confident”) and difficulty in performing the modification (0 = “not difficulty” and 10 = “most difficult/unable to perform”). A minimum of 10-minutes of daily walking will be requested to ensure enough data for the analysis.

Data processing and analysis

Marker-based motion capture data (as collected during the baseline and follow-up assessments) will be processed using commercially available software and using standard techniques our research group has established [5, 11, 19, 20]. Sensorized shoe data captured during the baseline and follow-up gait assessment, practice sessions, and at-home or community walking will be processed using custom MATLAB scripts. A trained research assistant, blinded to group allocation, will perform all data processing and analysis.

References

- [3] Richards R, van der Esch M, van den Noort JC, Harlaar J. The learning process of gait retraining using real-time feedback in patients with medial knee osteoarthritis. *Gait Posture.* 2018;62:1-6.

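### The secondary ANCOVA leaves out the stratification factors sex and KL grade, because its baseline-significance rule almost never admits them; the between-group tests are conservative and lose power if these factors are prognostic

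*SAP*

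**What the plan says.** The protocol's Randomization section allocates participants by a "block-stratified approach based on sex and KL grade".

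The SAP's opening paragraph says that baseline demographic data, with disease severity as one example, "will be examined for between-group differences using unpaired two-tailed t-tests", at the 0.05 level used throughout. Its Secondary Hypotheses paragraph then analyses biomechanical, clinical and difficulty change scores by ANCOVA "with significant between-group baseline demographic group differences and baseline outcome values included as covariates". Neither document says that sex or KL grade is always in the model. Disease severity is named only as something to be tested, and sex is not named at all.

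This ANCOVA serves two between-group hypotheses. H6 expects that biomechanical and clinical "change scores from baseline to follow up will not differ between groups". H4 includes lower difficulty ratings in the self-directed group. On when difficulty is measured, the protocol (Gait modification intervention) says that at the end of each practice session "they will be asked to rate the difficulty in achieving their FPA modification during that practice period"; a weekly rating at home is also collected.

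**The concern.** Design and analysis pull in opposite directions. Stratified blocking makes the arms alike on sex and KL grade, so a test for a baseline difference in either will almost never be significant, and the covariate rule will almost never include them. If they are prognostic, stratification has already reduced the true sampling variance of the group difference, but a model without them still counts their contribution as residual noise. The reported standard error is then too large and the test too cautious.

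At stake are power and precision, not bias or false positives. It matters most for H6, where the expected result is no difference: an inflated standard error makes a non-significant result easier to obtain. With about 30 people analysed there is little precision to spare.

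Separately, the sentence requires a baseline value for every outcome it covers, and difficulty has none.

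**Working it through.** **Inputs from the documents.** 36 randomized, 18 per group; 15% attrition; about 60% female; KL grade 2 or above (protocol, Participants); two-sided alpha 0.05 (SAP). The plan gives no power figure for the secondary ANCOVA. Its sample size is for the 2×4 interaction on the primary outcome: 30/0.85 = 35.3, taken up to 36. The 30 depends on an unstated correlation between repeated measures (about 0.68–0.70 reproduces it if sphericity holds; 0.5 gives 46). That does not affect this point. Here 30 are analysed, since 36 × 0.85 = 30.6.

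**Assumed inputs.** Permuted blocks of 4 within six sex × KL strata (the block size and KL grouping are not stated); KL 2/3/4 at 40/40/20%; 6 of 36 lost at random; R² split equally between sex and KL; d in units of the residual SD after baseline adjustment. Both factors are taken to be t-tested, which is generous to the SAP because sex is not named.

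**Step 1: how often the rule admits sex or KL.** Without stratification, two independent 5% tests would admit at least one in 1 − 0.95² = 9.75% of trials; simulation gives about 11%. With stratified blocks of size 2 to 6 it is 0.01% to 0.4% (about 0.1% for blocks of 4).

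**Step 2: expected effect on the standard error.** With n = 15 per arm and residual SD 1:

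- Factors omitted: SE ≈ √(2/15) = 0.365.
- Factors included, perfect balance: SE ≈ √(2/15) × √(1 − R²), which is 0.327 at R² = 0.2 and 0.305 at R² = 0.3.
- Ratio 1/√(1 − R²): 1.12 and 1.20.
- Type I error of the omitting model under perfect balance, 2[1 − Φ(1.96/√(1 − R²))]: 3.9%, 2.8% and 1.9% at R² = 0.1, 0.2 and 0.3.

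These are limits. Incomplete blocks and attrition leave some imbalance, so the real effect should be somewhat smaller.

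**Step 3: simulation.** 10,000 trials per scenario; Monte Carlo error about 0.5 points for power and 0.2 for type I error. The baseline outcome is in both models; the alternative always adds sex and categorical KL.

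| R² | Type I error, SAP rule vs always adjusted | Power at d = 0.8, SAP rule vs always adjusted |
|---|---|---|
| 0 | 5.1% vs 5.1% | 0.55 vs 0.52 |
| 0.1 | 4.5% vs 5.0% | 0.54 vs 0.56 |
| 0.2 | 3.8% vs 5.4% | 0.54 vs 0.62 |
| 0.3 | 2.7% vs 5.1% | 0.54 vs 0.68 |

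Mean model standard error is 0.375 vs 0.342 at R² = 0.2 (ratio 1.10) and 0.376 vs 0.320 at R² = 0.3 (ratio 1.18), just inside the limits in step 2. With a true d = 0.8, the chance of a non-significant H6 test is 1 − power: 46% vs 38% at R² = 0.2 and 46% vs 32% at R² = 0.3.

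For difficulty, with no baseline covariate, power is 0.56 vs 0.54 at R² = 0, 0.56 vs 0.63 at 0.2 and 0.56 vs 0.69 at 0.3.

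**Step 4: sensitivity.** At R² = 0.2 and d = 0.8, blocks of 2 give 0.54 vs 0.62, blocks of 6 give 0.53 vs 0.61, and a linear KL term gives 0.53 vs 0.62. A second simulation with KL at 40/35/25%, other block schemes and d = 1.0 gives type I error under the SAP rule of 3.6–3.9% at R² = 0.2 and 2.6–3.1% at 0.3. Power there is 0.74–0.75 vs 0.80–0.81 and 0.75–0.76 vs 0.85–0.86. At d = 0.35, the protocol's figure for a different outcome, power is 0.12–0.14 vs 0.14–0.18.

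**Step 5: difficulty.** The baseline assessment lists questionnaires, a stair climb and gait analysis, but no difficulty rating. Envelopes are opened after baseline testing and before the first practice session. The earliest rating therefore comes after randomization and may already reflect the assigned instruction, so it cannot serve as a baseline covariate.

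**The case against.** The strongest reply is that the harm rests on numbers the documents do not contain. R² must be what sex and KL explain after the baseline outcome is in the model, and that value may already absorb much of their effect. At R² = 0.1 the gain is 2 points; at R² = 0 adjustment costs up to 3. The effect size d = 0.8 is also assumed, and at d = 0.35 the trial has little power under either model. These are secondary outcomes in a trial titled exploratory, and the present rule neither biases the estimate nor inflates false positives. All of this stands and limits the size of the claim. It does not make the rule sound: an analysis should reflect how participants were randomized, and here the rule in effect ensures that it does not.

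Two further points also stand. H6's larger problem is reading non-significance as no difference; covariates do not cure that, since the adjusted model still misses d = 0.8 in 44%, 38% and 32% of trials at R² = 0.1, 0.2 and 0.3. And a replacement rule must state how KL is coded and which difficulty rating is analysed, or it leaves choices open. Both are details of the remedy.

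**Conclusion.** The concern holds. As written, the stratification factors are in effect never in the secondary ANCOVA, and the between-group tests for H6 and for difficulty in H4 are conservative whenever sex or KL grade is prognostic. At d = 0.8 with 30 analysed, the power given up is about 2, 8 and 14 points at R² = 0.1, 0.2 and 0.3; with no prognostic value there is nothing to gain and adjustment costs 1–3 points. The near-zero chance of admission was stable over the block sizes and KL splits tried; the power loss rests on assumed values of R² and d. The within-group changes in H5 are not affected. The missing baseline value for difficulty follows from the text and depends on none of these assumptions. The rule should be changed, but it does not invalidate the trial.

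**What to change.** Replace the covariate rule in the SAP's Secondary Hypotheses paragraph with:

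> The ANCOVA for each biomechanical and clinical change score includes group, the baseline value of that outcome, sex and KL grade, with KL grade coded as in the randomization strata. The model for difficulty, where no baseline value exists, includes group, sex and KL grade; the rating analysed is the one at (session or week, to be named). Baseline characteristics are reported descriptively, and baseline significance tests are not used to select covariates.

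The sponsor has to fill in the difficulty rating and confirm how KL was grouped for stratification.

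The cost is SAP wording only, since sex and KL grade are already collected. The model uses 2–3 error degrees of freedom (sex 1; KL 1 if linear, 2 if categorical). Age and BMI would no longer be adjusted for when they happen to differ at p < 0.05; if either is thought prognostic, it should be named in the same sentence before data are seen. The between-group mixed ANOVA for the primary hypotheses also omits sex and KL grade; it was not quantified here, but the SAP should treat both analyses consistently.

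### The SAP's covariate rule does not provide for the screening KAM response or the assigned toe direction, both known before randomisation; the screening response should be prespecified in the KAM ANCOVA

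*SAP*

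**What the plan says.** On the screen, the protocol (Gait screening) gives the purpose as follows, with the sentence's last word left off: "These data will be used to determine whether the participant is a responder to FPA modification, and which direction (toe-in or toe-out) elicits the greatest". A responder shows a KAM-impulse reduction of at least 5% for a 10° change in foot progression angle (FPA). People below that in both directions are excluded. Where both directions qualify, the one with the larger reduction per 10° is used. Each randomised participant therefore has a screening slope in the assigned direction.

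On allocation, the protocol (Randomization) places randomisation after eligibility and baseline testing, using a "block-stratified approach based on sex and KL grade".

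On analysis, the SAP (Secondary Hypotheses) applies ANCOVA to change scores for knee joint moments, pain, KOOS and difficulty, "with significant between-group baseline demographic group differences and baseline outcome values included as covariates". The SAP's opening section says that baseline demographics, with age, body mass index and disease severity as examples, are "examined for between-group differences using unpaired two-tailed t-tests". Neither document names the screening slope or the assigned direction as a covariate, stratification factor or subgroup.

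**The concern.** H6 predicts that KAM change scores will be alike in the two arms. Supporting that needs a narrow interval, and about 15 to 18 participants per arm will not give one easily. The trial already holds a measurement made to forecast how each knee's loading responds to foot rotation, and trusts it enough to decide who enters and which gait is trained. The SAP gives it no role in the analysis of that same loading.

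Assigned direction is a second fact known before allocation, and it defines the task each person practises. It is not balanced by design, so the arms can differ in their toe-in/toe-out mix by chance, and the plan has no stated way to show whether that matters. For difficulty the gap is wider: it is rated at practice sessions and weekly but is not among the listed baseline measures, so that model may have no baseline value to adjust for.

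At stake are the precision of a secondary comparison and the reader's ability to judge it. The primary outcome, performance error in SMOD, is not affected.

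**Working it through.** **Sample sizes.** The protocol states: "With power = 0.8 and alpha = 0.05, a total sample of 30 is required". Inflating for 15% attrition gives 30 / 0.85 = 35.3, rounded up to 36, as stated. The 30 itself depends on a correlation among the four repeated measures that is not given: with f = 0.175, a correlation of 0.5 needs 46, and 0.68 to 0.70 gives 30. That is a separate matter; N = 30 and N = 36 are taken as given here.

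**Other inputs.** The SAP states: "For all statistical analyses, alpha will be set to 0.05", so 95% intervals are used. The base model has group and baseline KAM, with N - 3 residual degrees of freedom. The documents give no correlation between screening slope and KAM change, no SD for KAM and no expected toe-in/toe-out split. So r, the partial correlation given baseline KAM, is an assumption shown as a range.

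**Effect of adding covariates.** For q added covariates,

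variance ratio = (1 - r²) × (N - 4) / (N - 4 - q)

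CI-width ratio = √(variance ratio) × t(0.975; N - 3 - q) / t(0.975; N - 3)

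The factor (N - 4)/(N - 4 - q) is the expected cost of chance covariate imbalance. The t ratio is the cost in degrees of freedom.

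Slope only (q = 1):

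- N = 30: factor 26/25 = 1.040; t ratio 2.0555/2.0518 = 1.0018. At r = 0.5, √(0.75 × 1.040) × 1.0018 = 0.885.
- N = 36: factor 32/31 = 1.032; t ratio 2.0369/2.0345 = 1.0012. At r = 0.5, √(0.75 × 1.032) × 1.0012 = 0.881.

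Change in CI width:

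| Assumed r | Slope, N = 30 | Slope, N = 36 | Slope + direction, N = 30 | Slope + direction, N = 36 |
|---|---|---|---|---|
| 0 | +2.2% | +1.7% | +4.5% | +3.5% |
| 0.3 | -2.5% | -3.0% | -0.3% | -1.2% |
| 0.5 | -11.5% | -11.9% | -9.5% | -10.3% |
| 0.7 | -27.0% | -27.4% | -25.4% | -26.1% |

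In the last two columns r is the joint partial correlation of both variables. Setting the width ratio to 1 gives break-even at about r = 0.2 for the slope alone (0.20 at N = 30, 0.18 at N = 36) and just under 0.3 for both (0.29 and 0.26).

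**Chance imbalance in direction.** Treat the toe-in counts as two independent Binomial(18, p) variables, with direction unrelated to the strata. A difference of at least 4 participants (4/18 = 22 percentage points) has probability 0.243 at p = 0.5 and 0.201 at p = 0.7. With 15 per arm, a difference of at least 3 (3/15 = 20 points) has probability 0.36 and 0.32.

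**Would the SAP's own test pick it up?** If direction were counted among the baseline characteristics and put through the unpaired t-test at 0.05, it would be admitted in about 5% of trials (4.6 to 6.5% over splits of 50:50 to 80:20 and 15 or 18 per arm). Most imbalances of 20 points would stay unadjusted.

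**The case against.** The strongest counter-argument is that the gain is unproven. No correlation is given, and several features of the design could make it small:

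- Entry is limited to responders of at least 5%, which restricts the range of the slope.
- The slope comes from one session of verbally guided passes, and direction is the better of two responses. The protocol itself allows for some regression.
- Baseline KAM is already in the model.
- KAM change also depends on how much FPA change each person achieves, and AMAC participants choose that for themselves. H4 expects smaller changes in AMAC than in SMOD, so a given slope may predict a larger KAM change in SMOD, and a single common coefficient would be only an approximation.

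All of this stands as reason for caution about r. It does not remove the case for the slope alone, because the worst-case cost is about 2% in interval width.

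A reader might infer three stronger things that the documents do not support. The first is that the SAP bars both variables outright. Its demographic list is introduced as examples and already includes disease severity, so the rule does not provide for them, but it cannot be said to exclude them in every reading. The second is that the KAM comparison certainly loses precision. Below about r = 0.2 the added slope slightly widens the interval, and a plain 1/(1 - r²) sample-size equivalent would overstate the gain at this size because it ignores the covariate's cost. The third is that unequal numbers of toe-in and toe-out participants bias the comparison. Under randomisation, chance imbalance causes no bias on average and no inflation of type I error. It affects a particular trial's estimate only if direction predicts the outcome, and neither document shows that it does.

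**Conclusion.** The point holds as a low-cost improvement to a secondary analysis in a trial titled exploratory. Both variables are fixed before randomisation, neither is a stratification factor, and the covariate rule names neither. The screening slope belongs in the KAM model because the protocol's own design treats it as predictive.

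The expected benefit runs from a loss of about 2% in interval width at r = 0, through a gain of 2.5 to 3.0% at r = 0.3, to about 12% at r = 0.5 and 27% at r = 0.7. These figures rest on an assumed r, a common slope across arms, and 30 to 36 analysed. The slope is measured on KAM impulse, while the SAP says only knee joint moments, so r may differ for other moment measures.

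The case for direction is weaker. A sizeable imbalance is fairly likely (0.20 to 0.24 for 4 or more participants with 18 per arm), but its consequences depend on an unknown prognostic effect. That supports a sensitivity analysis, not a required term in every model.

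**What to change.** Add to the SAP, Secondary Hypotheses, before any group-level data are examined: *The ANCOVA of KAM change will include, for all participants and regardless of any baseline test, the screening change in KAM impulse per 10° of FPA change in the assigned direction, in addition to the baseline outcome value. A sensitivity analysis will add assigned direction (toe-in or toe-out) to the KAM, pain, KOOS and difficulty models.*

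No new data are needed, since the screen must produce both values to decide eligibility and direction. The main KAM model loses one degree of freedom, and its interval widens by about 2% if the slope turns out to be uninformative. Fixing the choice in advance also removes any later question about why the covariate was or was not used.
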